17.1 Appendix 1: Subject Instructions41

17.2 Appendix 2: Training and Calibration of Clinical Examiners42

1. LIST OF ABBREVIATIONS

Acronym	Definition
AE	Adverse Event
ADE	Adverse Device Effect
ANOVA	Analysis of Variance
ANCOVA	Analysis of Covariance
BI	Bleeding Index
CFR	Code of Federal Regulations
CRF	Case Report Form
DMP	Data Management Plan
EDC	Electronic Data Capture
GCP	Good Clinical Practice
GI	Gingival Index
IRB	Institutional Review Board
FAS	Full Analysis Set
NA	Not Applicable
PI	Plaque Index
SADE	Serious Adverse Device Effect
SAE	Serious Adverse Event
SAP	Statistical Analysis Plan
SOP	Standard Operating Procedure
UADE	Unanticipated Adverse Device Effect
USADE	Unanticipated Serious Adverse Device Effect

3. PROTOCOL SUMMARY/SYNOPSIS

SYNOPSIS	
Sponsor	3M™ ESPE Dental Products
Study Title	A prospective, randomized, blinded, clinical study to evaluate effects of a 3M™ oral rinse on plaque and gingivitis.
Study ID number	EM # 11-050003
Purpose	The purpose of this study is to assess the performance of the 3M Oral Rinse.
Device Description	The 3M Oral Rinse contains an anti-plaque agent that provides a surface barrier to reduce the adhesion of dental plaque; thereby preventing the accumulation of dental plaque associated with gingivitis.
Device Intended Use	The 3M Oral Rinse is intended to help prevent and reduce plaque and gingivitis.
Treatment Groups	
 • 3M Oral Rinse • Placebo vehicle control • PerioShield™ Oral Health Rinse predicate device control • Placebo water negative control
Treatment Dose	Products will have identical instructions for use except for the predicate device that has a 10-mL dose rather than a 15-mL dose. Subjects will use the rinse twice a day for 30 seconds after tooth brushing.
Objective (primary efficacy endpoints)	
To evaluate the effects of the 3M Oral Rinse relative to the placebo vehicle control on plaque and gingivitis levels at 6 months, based on the following two parameters:
 
 • Lobene-Soparkar Modification of the Turesky Modified Quigley-Hein Plaque Index (PI) • Löe-Silness Gingival Index (GI)

Objectives (secondary efficacy and safety endpoints)
	
 • To evaluate the 3M Oral Rinse: 
 ○ Versus placebo vehicle control at 3 months using Modified Quigley-Hein Plaque Index (PI) scores. ○ Versus placebo vehicle control at 3 months using Löe-Silness Gingival Index (GI) scores. ○ Versus placebo vehicle control at 3 and 6 months using Eastman Interdental Bleeding Index (BI) scores. • To assess the safety of the 3M oral rinse by tracking abnormal changes to soft and hard tissues, and adverse events during the study. • To conduct pairwise comparisons among the four treatment groups, namely, 3M Oral rinse, vehicle control, PerioShield (predicate) and water control, based on the PI and GI scores at 6 months.

Study Design
	
The study is a prospective, randomized, single center, parallel group, blinded clinical trial. Subjects will be randomly assigned to one of the four treatment groups.


Study Duration
	
The duration of subject involvement is approximately 6 months.
 
Study duration from the time of first subject enrolled until last subject completed is expected to be approximately 12-15 months.

Sample Size
	
The sample size was estimated based on GI and PI scores from preliminary clinical study data and the literature. It is estimated that 34 subjects per group will provide 90% power to detect a difference of 0.40 (standard deviation (SD) of 0.5) in the GI and PI scores using a 1-sided 0.025 alpha level. To account for possible dropouts, a sample size of 50 subjects per group will be recruited.

Screening Inclusion criteria:	Subjects to whom these criteria apply will be entered into the 7-day washout 
• Able to understand and willing to sign the Informed Consent• In good general health ages 18 and older• Have at least 20 natural teeth, including at least one molar and one premolar in each quadrant but excluding the third molars• Willing to return to the study facility for scheduled study visits and recalls• Agree not to use other oral hygiene products (non-study toothpaste, dental floss, mouth rinse, chewing gum)• Agree not to brush or floss teeth after 10:00 pm the night before and not eat or drink 4 hours before an appointment• Agree to the study instructions and visit schedule, including no eating or drinking for 4 hours before assessment appointments
--------------------------------------	---


Screening Exclusion criteria:
	
Subjects to whom these conditions apply will be excluded:
 
 • A history of antibiotic therapy within the previous 30 days or have a condition that is likely to need antibiotic treatment over the course of the study (eg, cardiac conditions requiring antibiotic prophylaxis such as heart murmurs, pacemakers, or prosthetic heart valves, and prosthetic implants) • A history of using antimicrobial oral mouth rinse during the past 3 months • Taking medications which may alter gingival appearance/bleeding • Use of anticonvulsants, calcium channel blockers, or other medications with side effects known to impact oral health • Current participation in any other clinical study within the past 30 days • Reside in the same household with a subject already enrolled in the study • Dry mouth due to head/neck radiation therapy • Orthodontic appliances • Widespread caries or chronic neglect • Gross pathological changes of oral soft tissues • Known history of sensitivity to oral hygiene products • Advanced periodontal disease (purulent exudate, tooth mobility, and/or extensive alveolar bone loss) • Pregnant or nursing or plan to become pregnant within the 6-month study duration • Medical and oral conditions that, in the investigator's judgment, may compromise the subject's safety or interfere with the conduct and outcome of the study • Difficult to be compliant with study visits, such as extensive travel commitments or lack of transportation

Baseline Inclusion/exclusion criteria:
	
Subjects must meet the screening inclusion criteria and these additional requirements:
 
 • Completed the washout period (at least 7 days) using only the study toothbrush, dental floss and toothpaste • A qualifying baseline GI of at least 1.0, as determined by the Löe-Silness Gingival Index (GI) • A qualifying baseline Modified Quigley-Hein (Lobene-Soparkar Modification of Turesky's modification) Plaque

	
Index (PI) of at least 1.5
 
Subjects will be excluded if they do not meet the screening exclusion criteria.

Randomization	
200 subjects will be randomized to one of the four treatment groups.

Blinding:	
The Principal Investigator and clinical examiners will be blinded to the treatment products. No clinical examiners will see the allocated rinse assigned per the randomization schedule. Due to the rinse packaging differences and to maintain the blind, all study products will be placed in a non-transparent container. Subjects will be told not to open the container until they return to their home and to bring study supplies back to their next scheduled appointment in the same container. Only the study coordinator at the site will know the randomization assignment.

Outcome Measures:	
 • Modified Quigley-Hein Plaque Index at baseline, 3 and 6 months (\pm 10 days) • Löe-Silness Gingival Index at baseline, 3 and 6 months (\pm 10 days) • Eastman Interdental Bleeding Index at baseline, 3 and 6 months (\pm 10 days) • Oral soft and hard tissue assessment baseline, 3 and 6 months (\pm 10 days) • Adverse Events
Study Restrictions	
Subjects will only use the study toothpaste, toothbrush, dental floss and mouth rinses that are provided by the study staff and will refrain from using any other oral hygiene products or measures such as other toothpaste, mouth rinse, mechanical toothbrush and chewing gum etc.
 
Subjects will not eat or drink 4 hours before clinical exams, and will not brush or floss their teeth the night before and the morning of the clinical exams.

Clinical Safety Assessment	
Safety assessments will be completed by a clinical examiner at each clinical visit.

Data Analysis Plan:	
Means and standard deviations will be calculated for all clinical measurements and assessments. Categorical variables will be summarized in frequency distributions. Analysis of variance (ANOVA) or (ANCOVA) will be used to test for treatment group differences between the subject groups at 3 and 6 months.
 
GI, PI, and BI scores will be calculated as the average tooth score across all teeth as one score per patient, per visit.
 
All statistical analyses will be performed using SAS version 9.3 or above (SAS Institute, Cary, NC) or another statistical software package.

----------------------------	--

Study Schedule						
	Screening followed by at least a 7-day washout	Baseline	Interim Visits (Approximately) 1.5 and 4.5 months	3-Month (\pm 10 days)	6-Month (\pm 10 days) or upon subject discontinued	Unscheduled visit can occur at any time for any reason
Informed Consent/ Screening Inclusion/ Exclusion Demographics	X					
Baseline Inclusion/ Exclusion/		X				
Oral Exam		X		X	X	X
Concomitant Medications		X	X	X	X	
Randomization		X				
Modified Quigley-Hein Plaque Index		X		X	X	
Löe-Silness Gingival Index		X		X	X	
Eastman Interdental Bleeding Index		X		X	X	
Adverse Events		X	X	X	X	X
Assessment of Compliance		X	X	X	X	
Subject Diary Review/Collection			X	X	X	
Prophylaxis		X				
Review Instructions		X	X	X		X
Blinding Assessment		X			X	
Replenish Study Supplies		X	X	X		

4. BACKGROUND INFORMATION AND SCIENTIFIC RATIONALE

4.1 Background

Gingivitis is most commonly seen as a plaque-induced, inflammatory condition of the gum tissues that affects approximately 50% to 90% of the population.^{1,2} Plaque biofilm can include viruses, fungi, mycoplasma and even protozoa but bacteria are the prominent species.³ One concern is that gingival inflammation (ie, gingivitis) caused by the plaque biofilm has the potential to spread into the underlying supporting structures of the teeth resulting in the more destructive condition called periodontal disease. Agents that interfere with bacterial adhesion and disrupt biofilm formation may aid in plaque control, thereby reducing the level of inflammation and gingivitis. While they are not meant to replace tooth brushing these rinses could serve as valuable adjuncts to conventional oral hygiene procedures.^{3,4} Many oral rinses contain anti-bacterial agents to reduce gingivitis for example chlorhexidine digluconate (CHX), which remains the standard for chemical antiplaque rinses, but is generally not used long-term due to side effects. Ideally, antiplaque methods of preventing and reducing biofilm especially when used long term should not allow opportunistic pathogens to colonize the oral environment.⁵

4.2 Rationale

The 3M Oral Rinse contains an anti-plaque agent that provides a surface barrier to reduce the adhesion of dental plaque. 3M Oral Rinse is intended to help prevent and reduce plaque and gingivitis. The rinse serves as an adjunct to normal mechanical oral hygiene.

The 3M rinse is subject to 21 CFR 872.5580 and the FDA Guidance: *Class II Special Controls Guidance Document: Oral Rinse to Reduce the Adhesion of Dental Plaque*.

The proposed study will have 4 study arms/treatment groups and will assess the performance of the 3M Oral Rinse over a 6- month period.

4.3 Name, Description and Intended Use of the Investigational Product

The 3M Oral Rinse contains a [REDACTED] surfactant using a proprietary formula. The intended use of the product is to help prevent and reduce plaque and gingivitis.

4.4 Risk/Benefit Summary

4.4.1 Risks and Benefits of the Experimental Device and Clinical Investigation

The anticipated clinical benefit of the 3M Oral Rinse and the predicate oral rinse is control of plaque and gingivitis. Subjects who receive placebos may not receive the same benefit as those who receive active treatment.

Subjects will be instructed to refrain from any dental treatment, including dental prophylaxis, during the study. If necessary, emergency dental treatment may be performed. Subjects will be instructed to inform the investigator as soon as possible if any emergency dental treatment is performed. The investigator will then decide whether the subject should continue in the study. Subjects who receive medical and/or dental treatment with antibiotic management may be dropped from the study.

The following is a list of potential risks associated with this study.

- Plaque and gingivitis may not improve
- Subjects may have an increased risk of disease or infection from altered oral mucosal immunity due to potential changes in oral flora
- Potential allergies to product components
- Oral rinses can cause transient mouth/tongue numbness
- Oral rinses can cause mucosal sloughing/irritation
- Oral rinses can cause transient dry mouth
- Oral rinses may cause transient alteration in taste
- Subjects may experience bleeding gums during study visits with clinicians due to probing/gingivitis assessment procedures
- Subjects should avoid rinse contact with skin and eyes. In case of contact with skin, wash thoroughly and in case of contact with eyes, flush with water.

5. Study Design and Study Objectives/Endpoints

5.1 Study Design

This is a prospective, single site, randomized, parallel, blinded clinical trial. Subjects will be randomly assigned to one of four treatment groups identified as Product A, Product B, Product C or Product D.

Subjects will be screened for eligibility and entered into a washout period that is at least 7 days, during which time they will be provided with study toothbrush, toothpaste and dental floss. No oral rinses or medication that alters oral tissue health will be used or taken during the washout period. After randomization, the designated rinse will be placed into a non-transparent container so that other subjects and clinical examiners do not see the allocated rinse per the randomization schedule.

Subjects will be provided with both verbal and written instructions to take home, and a diary for tracking dosing compliance and any side effects from rinse use. Subjects will return the diary along with the empty/used/unused rinse bottles in the original container at their next scheduled visit to monitor for compliance of product use. Subjects that are found to be non-compliant will remain in the study, be re-trained and documented accordingly.

Examinations for the clinical endpoints (PI, GI and BI) will be conducted at the baseline, 3-month (± 10 days), and 6-month (± 10 days) visits.

Interim visits will be scheduled to review diary, replenish study supplies, check study compliance, etc. Subjects will be provided Colgate Regular toothpaste, dental floss and a soft toothbrush (replaced at 3 months) for use during the 6-month study period.

5.2 Primary Efficacy Objective with 3M Oral Rinse and Vehicle Control

To investigate the effects of the 3M Oral Rinse relative to the placebo vehicle control on plaque and gingivitis levels, at 6 months, based on the Modified Quigley-Hein Plaque Index (PI) and the Löe-Silness Gingival Index (GI) scores.

5.3 Secondary Efficacy Objective with 3M Oral Rinse and Vehicle Control

- To investigate the effects of the 3M Oral Rinse vs. Placebo Vehicle Control on plaque and gingivitis, at 3 months, based on the Modified Quigley-Hein Plaque Index (PI) and the Löe-Silness Gingival Index (GI) scores.
- To investigate the effects of the 3M Oral Rinse vs. Placebo Vehicle Control on Eastman Interdental Bleeding Index (BI) scores at 3 and 6 months

5.4 Secondary Efficacy Objective with All Four Treatment Groups

To investigate the relative efficacy, using pairwise comparisons, of the four treatment groups, namely 3M Oral rinse, vehicle control, PerioShield (predicate) and water control, with respect to the PI and GI scores at 6 months.

5.5 Safety Objectives/Endpoints

- To assess the safety of the 3M oral rinse by tracking abnormal changes to soft and hard tissues, reported side effects and adverse events during the study.

6. SUBJECT SELECTION

Subjects will come in for a screening visit and if they meet the inclusion criteria they will be scheduled for baseline measures after at least a 7-day washout period.

6.1 Subject Inclusion Criteria at Screening

Subjects to whom all of these conditions apply will be eligible for the washout period of this study:

- Able to understand and willing to sign the Informed Consent
- In good general health ages 18 and older
- Have at least 20 natural teeth, including at least one molar and one premolar in each quadrant but excluding the third molars
- Willing to return to the study facility for scheduled study visits and recalls
- Agree not to use other oral hygiene products (eg, non-study toothpaste, dental floss, mouth rinse, chewing gum)
- Agree not to brush or floss teeth after 10:00 pm the night before an appointment
- Agree to the study instructions and visit schedule, including no eating or drinking for 4 hours before assessment appointments

6.2 Subject Exclusion Criteria at Screening

Subjects to whom any of these conditions apply will be excluded:

- A history of antibiotic therapy within the previous 30 days or have a condition that is likely to need antibiotic treatment over the course of the study (eg, cardiac conditions requiring antibiotic prophylaxis such as heart murmurs, pacemakers, or prosthetic heart valves, and prosthetic implants)

- A history of using antimicrobial oral mouth rinse during the past 3-months
- Taking medications which may alter gingival appearance/bleeding
- Use of anticonvulsants, calcium channel blockers, or other medications with side effects known to impact oral health
- Current participation in any other clinical study within the past 30 days
- Reside in the same household with a subject already enrolled in the study
- Dry mouth due to head/neck radiation therapy
- Orthodontic appliances
- Widespread caries or chronic neglect
- Gross pathological changes of oral soft tissues
- Known history of sensitivity to oral hygiene products
- Advanced periodontal disease (purulent exudate, tooth mobility, and/or extensive alveolar bone loss)
- Pregnant or nursing or plan to become pregnant within the 6-month study duration
- Medical and oral conditions that, in the investigator's judgment, may compromise the subject's safety or interfere with the conduct and outcome of the stud
- Difficult to be compliant with study visits, such as extensive travel commitments or lack of transportation

6.3 Baseline Inclusion Criteria at Enrollment

Subjects who meet the screening inclusion criteria and the following baseline inclusion criteria apply will be eligible for treatment randomization:

- Completed the washout period (at least 7 days) using only the study toothbrush, dental floss and toothpaste
- A qualifying baseline Gingival Index of at least 1.0, as determined by the Löe-Silness Gingival Index (GI)
- A qualifying baseline Modified Quigley-Hein (Lobene-Soparkar Modification of Turesky's Modification) Plaque Index (PI) of at least 1.5 (referred to as Modified Quigley-Hein Plaque Index in the following text)

6.4 Baseline Exclusion Criteria at Enrollment

At the baseline visit the same exclusion criteria as the screening visit must be met prior to randomization.

6.5 Recruitment

The clinical site has a racially and ethnically diverse database that may be used to identify potential subjects. In addition, advertisements in publications or the local newspapers may be placed to enhance subject recruitment. The advertisements will provide a brief synopsis of the study and instruct potential subjects to contact the study site for more information. If the subject is interested in participating, he or she will be scheduled for the screening appointment. Subjects who go through the consenting process, meet the Inclusion/Exclusion criteria, and sign an Informed Consent form will be screened for the study and begin the washout. If they qualify at baseline they will be randomized. Multi-language consent forms will be prepared to meet the local IRB requirements, if necessary.

6.6 Withdrawal or Termination of Subjects

A genuine effort will be made to collect all outcome data and keep subjects enrolled in the study. Effort will be made to determine the reason(s) why a subject fails to return to the study site for the necessary visit(s) or has dropped from the study. A subject may withdraw from the study at any time.

A subject may be dropped from the study if any of the following occur:

- Subject fails to show up at the scheduled visits (three attempts will be made to schedule subjects and if they have not responded they will be dropped)
- Subject elects to terminate participation in the study
- Investigator or Study Coordinator elects to withdraw the subject (with written justifications about safety, noncompliance or any other reason)
- Subject experiences a severe adverse reaction to the test product(s)
- Subject begins long-term (12 days or more) treatment with antibiotics
- Subject needs dental therapy that cannot wait until the end of the study
- Subject becomes pregnant

Subjects discontinued from the study for any reason will not be allowed to reenter the study. Subjects withdrawn due to adverse events (AEs) will receive follow-up until the AE is resolved, or is determined by the Investigator to be stable. Final assessments will be completed if possible.

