5.2 Intent-To-Treat Population

The intent-to-treat (ITT) data set will be the primary efficacy data set and will include all subjects randomized to a treatment group. Subjects will be analyzed in the group to which they were randomly assigned. Subjects with missing post-baseline PI and/or GI data will be included in the ITT analysis using appropriate input data sets and imputation methods. The Expectation-Maximization (EM) algorithm will be used, and this procedure assumes the data will be multivariate normal and missing at random. If these assumptions prove to be violated, other methods will be considered.

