8. STUDY PROCEDURES/EVALUATIONS

8.1 Scheduled Study Visits

8.1.1 Screening Visit

- Informed consent
- Screening inclusion/exclusion criteria
- Demographics
- Distribute study toothbrush, toothpaste and dental floss to use for washout (at least 7-days)

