11.8 Sample Size

The sample size was estimated based on GI and PI scores from the preliminary data (CR 14-006) and from the FDA approval documents obtained under Freedom of Information for the predicate

device, Decapinol Oral Rinse, manufactured by Sinclair Pharmaceuticals (identical product now marketed as PerioShield Oral Health Rinse in the US by Sunstar Americas, Inc.)¹³

It is estimated that 34 subjects per group will provide 90% power to detect a difference of 0.40 (standard deviation (SD) of 0.5) in the GI and PI scores using a 1-sided 0.025 alpha level. To account for possible dropouts, a sample size of 50 subjects per group will be recruited.

It is anticipated that 200 subjects enrolled, with 50 subjects in each of the four groups will provide adequate power for the study endpoints. Subjects who drop out will not be replaced. Each subject will be asked to return to the study clinic around the middle of the two recalls (1.5 and 4.5 months) for study product replenishment, assessment of diaries, concomitant medications and reinforcement of product use instructions.

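### Protocol 6.6 conflicts with itself on non-responders: one reading ends outcome follow-up after a missed interim visit, and nothing keeps the month-6 PI/GI examination open to them

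*Combined protocol and SAP*

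**What the plan says.** Protocol section 6.6 opens with a retention commitment: "A genuine effort will be made to collect all outcome data and keep subjects enrolled in the study". Its list of grounds for removal is introduced permissively: "A subject may be dropped from the study if any of the following occur". The first item is "Subject fails to show up at the scheduled visits", with a parenthesis in mandatory terms: "three attempts will be made to schedule subjects and if they have not responded they will be dropped". After the list comes a bar on return: "Subjects discontinued from the study for any reason will not be allowed to reenter the study".

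The item does not define which visits it means. The protocol's heading "8.1 Scheduled Study Visits" covers the two interim visits (8.1.3 and 8.1.5) as well as baseline, month 3 and month 6. Section 11.8 describes the interim visits: "Each subject will be asked to return to the study clinic around the middle of the two recalls". They cover diary and compliance review, concomitant medications, instructions and resupply, and the study schedule adds adverse events. PI, GI and BI are not scored there.

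Two provisions point towards keeping data. Section 6.6 ends by providing for final assessments where feasible, and the schedule's month-6 column also applies when a subject is discontinued.

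On the analysis side, the ITT set in SAP 5.2 "will include all subjects randomized to a treatment group". SAP 6.2 and 6.3 impute missing PI and GI by the EM algorithm within arm, under multivariate normality and missing at random. SAP 5.3 removes from the per-protocol set anyone without a 6-month PI or GI score.

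**The concern.** Section 6.6 gives the site two instructions for the same subject. One is to try to collect every outcome, with removal as an option. The other is to drop the subject after three unanswered attempts, with no return. A site that follows the second, and that counts interim visits as scheduled visits, could close the file on someone who went silent around month 1.5, about 4.5 months before the co-primary examination. That person might have been reachable again by month 6.

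What is at stake is an observed month-6 score replaced by an imputed one. People who stop answering the site may well differ in adherence and hygiene from those who keep attending. The imputation draws on relations estimated mainly from attenders, so it is least secure for this group. These subjects also leave the per-protocol set, and section 11.8 does not replace dropouts.

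**Working it through.** **1. The text, side by side**

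| Question | Towards keeping the subject | Towards removal |
|---|---|---|
| Is dropping optional? | List introduced with *may* (6.6) | Parenthesis says *will* (6.6) |
| Are outcomes still sought? | Opening sentence of 6.6; final assessments where feasible; schedule column at discontinuation | No re-entry for any reason (6.6) |
| Which visits count? | Plural and undefined; the paragraph above the list speaks of necessary visits | Heading of 8.1 includes both interim visits |

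No section says whether a subject dropped for non-response is invited to the month-6 examination, or how an examination at discontinuation is assigned to a time point. A non-responder cannot be examined when dropped. An examination at that moment would in any case not be a month-6 score.

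**2. What the imputation would have to work with**

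A subject dropped at month 1.5 has baseline scores only. One dropped at month 4.5 has baseline and month-3 scores, provided month 3 was attended. For the first, the LOCF sensitivity analysis carries forward a baseline score taken before the professional cleaning that ends the baseline visit (protocol 8.2.2). The group-mean analysis borrows from attenders again.

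**3. The plan's sample size**

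Inputs (protocol 11.8, SAP 6.1): difference 0.40, SD 0.5, one-sided alpha 0.025, 90% power, 34 per group needed, 50 recruited. Two-sample t-test with noncentrality (0.40/0.5) × √(n/2):

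- n = 33: power 0.893
- n = 34: power 0.902, so the stated 34 is reproduced
- n = 50: power 0.977

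The implied allowance for loss is (50 − 34)/50 = 32%. No dropout rate is stated.

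**4. Effect on power**

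With 10% loss (n = 45), per-endpoint power is 0.9635. Power for both co-primaries, if they were independent, falls from 0.9773² = 0.955 to 0.9635² = 0.928. Positive correlation would raise both figures.

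**5. Possible shift in the estimate**

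The documents give none of these three inputs, so they are assumptions:

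- 4–10% of one arm meets the rule: 50 × 0.04 = 2 to 50 × 0.10 = 5 subjects
- half of them could be examined at month 6: 1 to 2.5 subjects, or 2–5% of the arm
- true and imputed scores differ by 0.4, in that arm only; this equals the whole planned treatment difference, so it is generous

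Avoidable shift = recoverable fraction × gap:

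- low end: 0.02 × 0.4 = 0.008
- high end: 0.05 × 0.4 = 0.02

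The unadjusted standard error at 50 per arm is 0.5 × √(2/50) = 0.10. The shift is therefore 0.08 to 0.2 of a standard error, or 2–5% of the 0.40 target. It scales linearly: a gap of 0.2 would halve it. Equal rates and gaps in both arms would largely cancel.

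**The case against.** The strongest reply is that the plan already leans towards retention. The list is permissive, the section opens with a commitment to collect outcomes, and the schedule provides PI, GI and BI at discontinuation. The item needs three unanswered attempts, not just a missed appointment, and someone who never responds yields no score under any rule. Dropped subjects remain in the ITT set with imputation, section 13.1 uses data already collected from withdrawn subjects, and two sensitivity analyses are planned. The time at which a site declares loss to follow-up is partly an operational choice.

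Much of this stands, and it rules out several stronger readings that a reader might infer:

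- *Any single missed visit forces removal, so primary scores are given up by rule.* The text is contradictory, not clear-cut. The visits are plural and undefined, and reaching the interim visits requires joining the item to the heading of 8.1.
- *The interim visits are for supplies only.* They also cover diary, compliance and medication review and, in the schedule, adverse events.
- *The rule breaks the ITT principle.* Dropped subjects stay in the ITT set. What may be lost is their observed score.
- *The shift is 0.02–0.04.* That figure applies the 0.4 gap to 5–10% of an arm, including people whom no follow-up rule could recover.

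The reply does not close the gap. An examination at discontinuation cannot reach a non-responder, it is not a month-6 score, and the re-entry sentence stands in the way of one later. Imputation and the two sensitivity analyses do not replace an observation.

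**Conclusion.** The point holds as an internal conflict with a modest consequence. Section 6.6 both promises outcome collection and, on one reasonable reading, ends it after three unanswered attempts at a visit where no efficacy index is scored. The month-6 PI and GI examination is not expressly kept open to these subjects.

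Under the stated assumptions the avoidable shift is about 0.008–0.02, against a standard error of about 0.10. The number of recoverable scores cannot be derived from the documents. Power is not affected to any degree that matters: up to 32% loss still leaves 90% per endpoint. The reason to act is less reliance on a missing-at-random assumption, at almost no cost, in a trial where both co-primaries must succeed. This is a worthwhile improvement and not a threat to the trial's validity.

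**What to change.** Amend section 6.6 of the protocol:

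- Reconcile *may* and *will* in the missed-visit item.
- After three unanswered attempts, record the visit as missed and keep the subject in outcome follow-up unless consent is withdrawn.
- Try again in the 3-month and 6-month windows (each ±10 days), and classify as lost to follow-up only after the 6-month window closes.
- State that the re-entry bar does not prevent PI, GI and BI outcome examinations.

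Whether product is resupplied in the meantime is left to the sponsor, and the other grounds for withdrawal are untouched.

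The cost is a short amendment and a few more contact attempts by existing staff. There is one downside. Some month-6 scores will come from subjects who were without rinse for a time. That fits an analysis by randomized group, but it may dilute the estimated effect slightly.
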